ALT	Alanine aminotransferase (SGPT)
ANCOVA	Analysis of Co-variance
ANOVA	Analysis of Variance
AST	Aspartate aminotransferase (SGOT)
AUC	Area under concentration-time curve
AUC(0-∞)	Area under the concentration-time curve from time zero (pre-dose) extrapolated to infinite time
%AUCex	Percentage of AUC(0-∞) obtained by extrapolation
AUC(0-x)	Area under the concentration-time curve from zero (pre-dose) to some fixed nominal time x
AUC(0-t)	Area under the concentration-time curve from time zero (pre-dose) to last time of quantifiable concentration within a subject across all treatments
AUC(0-τ)	Area under the concentration-time curve over the dosing interval
β-HCG	Beta-Human Chorionic Gonadotropin
BA	Bioavailability
BE	Bioequivalence
BMI	Body mass index
BP	Blood pressure
BPM	Beat Per Minute
BQL	Below the quantification limit
BUN	Blood urea nitrogen
CBC	Complete blood count
CDISC	Clinical Data Interchange Standards Consortium
CI	Confidence Interval
CIB	Clinical Investigator's Brochure
CL _r	Renal clearance
CL	Systemic clearance of parent drug
CL/F	Apparent clearance following oral dosing
C _{max}	Maximum observed concentration
C _{min}	Minimum observed concentration
C _τ	Pre-dose (trough) concentration at the end of the dosing interval
C _t	Last observed quantifiable concentration
CDMP	Clinical Document Management and Publishing
CO ₂	Carbon dioxide
CPDM	Clinical Pharmacology and Discovery Medicine
CPK	Creatine phosphokinase
CPKMS	Clinical Pharmacokinetics Modelling & Simulation
CPSR	Clinical Pharmacology Study Report
CP-RAP	Clinical Pharmacology Reporting and Analysis Plan

CONFIDENTIAL

CM2009/00071/00

PWH115760

CRF	Case Report Form
CRO	Contract Research Organization
CRU	Clinical Research Unit
CV	Coefficient of variance
DBP	Diastolic blood pressure
DDS	Drug Development Sciences
DMPK	Discovery Medicine Pharmacokinetics
ECG	Electrocardiogram
ECP	Endothelial Progenitor Cell
EDC	Electronic data capture
EISR	Expedited Investigator Safety Report
EPO	Erythropoietin
Fabs	Absolute bioavailability of drug determined following extravascular and intravascular dosing
FDA	Food and Drug Administration
Fr _{el}	Relative bioavailability of drug determined between two formulations of the same drug following similar or different extravascular route of administration
FSH	Follicle Stimulating Hormone
FTIH	First time in humans
GCP	Good Clinical Practice
GCSP	Global Clinical Safety and Pharmacovigilance
GGT	Gamma glutamyltransferase
GLS	Geometric Least-Squares
GSK	GlaxoSmithKline
HARP	GSK system designed to aid the statistical analysis of clinical trials data (Phases I to IV).
hCG	Human chorionic gonadotropin
HIV	Human Immunodeficiency Virus
h/hr	Hour(s)
HR	Heart rate
IB	Investigator's Brochure
ICH	International Conference on Harmonization of Technical Requirements for Registration of Pharmaceuticals for Human Use
IDMC	Independent Data Monitoring Committee
IDS _L	Integrated Data Standards Library
IEC	Independent Ethics Committee
IND	Investigational New Drug
IP	Investigational Product
IRB	Institutional Review Board
IU	International Unit
IV	Intravenous
Kg	Kilogram

CONFIDENTIAL

CM2009/00071/00

PWH115760

λ_z	Terminal phase rate constant
L	Liter
LFTs	Liver function tests
Ln	Naperian (natural) logarithm
LOQ	Limit of quantification
LLQ	Lower limit of quantification
μg	Microgram
μL	Microliter
MAT	Mean absorption time
MedDRA	Medical Dictionary for Regulatory Activities
Mg	Milligrams
mL	Milliliter
MRT	Mean residence time
MSDS	Material Safety Data Sheet
Msec	Milliseconds
NQ	Non-quantifiable concentration measured as below LLQ
PAH	Pulmonary Artery Hypertension
PASP	Pulmonary Artery Systolic Pressure
PHD	HIF- proly hydroxylases
PD	Pharmacodynamic
PGx	Pharmacogenetics
PK	Pharmacokinetic
PSRI	Periodic Safety Reports for Investigators
QC	Quality control
QD	Once daily
RAP	Reporting and Analysis Plan
RBA	Relative Bioavailability
RBC	Red blood cells
RV	Right Ventricular
SAE	Serious adverse event(s)
SAS	Statistical Analysis Software
SD	Standard deviation
SDTM	Study Data Tabulation Model
SOP	Standard Operating Procedure
SPM	Study Procedures Manual
SUSAR	Suspected, Unexpected, Serious Adverse drug Reaction
T	Infusion duration
T	Time of last observed quantifiable concentration
$t\frac{1}{2}$	Terminal phase half-life
T	Dosing interval
Tlag	Lag time before observation of drug concentrations in sampled matrix
Tlast	Time of last quantifiable concentration

CONFIDENTIAL

CM2009/00071/00

PWH115760

Tmax	Time of occurrence of Cmax
ULN	Upper limit of normal
UK	United Kingdom
US	United States
Vd/F	Apparent volume of distribution after extravascular (e.g., oral) administration
WBC	White blood cells

Trademark Information

Trademarks of the GlaxoSmithKline group of companies	Trademarks not owned by the GlaxoSmithKline group of companies

PWH115760

1. INTRODUCTION

The purpose of this reporting and analysis plan (RAP) is to describe the analyses to be included in the Clinical Pharmacology Study Report for Protocol:

Revision Chronology:		
2011N121462_00	2012-Mar-20	Original
2011N130130_01	2012-NOV-21	Amendment No.:01 This amendment reflects changes to the patient eligibility criteria, stopping criteria and sampling time points per regulatory feedback.
2011N130130_02	2013-FEB-14	Amendment No.: 02 This amendment reflects changes to DFU patient eligibility criteria number 7 and screening procedures in Part A as well as minor edits for clarity.
2011N130130_03	2013-JUN-06	Amendment No.: 03 This amendment clarifies an eligibility criterion and DFU clinical assessments as well as minor edits for clarity.
2011N130130_04	2014-JAN-29	Amendment No.: 04 This amendment reflects changes in the container type used to supply the bulk ointment. Minor edits are also included for clarity.
2011N130130_05	2014-JUN-02	Amendment No.: 05 This amendment reflects modifications to the DFU inclusion and exclusion criteria, hemoglobin stopping criteria and a change in biopsy collection expectations. Minor edits are also included for clarity. Amendment 5 was republished before distribution, with the DNG number of 2011N130130_06, in order to correct an error.
2011N130130_07	2014-NOV-19	Amendment No. 06: Due to emerging data, specific areas of Part B of the protocol were redesigned to better meet the needs of the study. To date Part A GSK1278863 systemic exposure is below analytical limits of quantification and therefore the stand alone single dose

PWH115760

		assessment in Part B is no longer required. Exclusion criteria number 10 was adjusted to better reflect the patient population. Other minor edits were also included for clarity.
PWH115760 RAP_V11	2017-SEP-19	Amendment No. 07 Due to the termination of this indication some TLF's were deleted in order to streamline outputs
PWH115760 RAP_V13	2017-OCT-1	Amendment No. 08 Text revisions to correspond with the TLF revisions in the prior amendments. Additional TLF's added in order to comply with data disclosure.

All decisions regarding final analysis, as defined in this RAP document, have been made prior to Database Freeze (unblinding) of the study data.

2. STUDY OBJECTIVE(S) AND ENDPOINT(S)

2.1. Study Objectives

2.1.1. Primary Objectives

- To evaluate the safety and tolerability of the topical application of GSK1278863 in healthy volunteers and patients with diabetic foot ulcer following single dose (SD) and repeat dose (RD) administration.
- To determine the pharmacokinetics of single and repeat doses of GSK1278863 and its metabolites following SD and RD administration.

2.1.2. Exploratory Objectives

To evaluate the effect of single and repeated doses of GSK1278863 on:

- Gene expression for HIF targets and genes associated with wound healing in the DFU.
- Local levels of biomarkers (e.g. inflammatory panel for cytokines, proteases).
- Bioburden in the wound (e.g. rtPCR for bacterial load).
- Physical characteristics of the wound (e.g. rate of healing, wound volume).
- Clinical characteristics of the wound (e.g., exudate, granulation tissue, color).

To evaluate the effect of repeat doses of GSK1278863 on:

- Gene expression for HIF targets and genes associated with wound healing in the DFU.
- Local levels of biomarkers (e.g., inflammatory panel for cytokines, proteases, inflammatory cell counts, collagen turnover).
- Bioburden in the wound (e.g., rtPCR for bacterial load).
- Biomarkers of angiogenesis via blood flow and oxygen availability [e.g., skin perfusion pressure (SPP) and pulse volume (PV), hyperspectral imaging].
- Tissue concentrations of GSK1278863 after repeat dosing in selected subjects, as site capabilities to perform the assessment permit.
- Circulating biomarkers for HIF activation (e.g., hemoglobin, hepcidin, EPO).
- Physical characteristics of the wound (e.g. rate of healing, wound volume).
- Clinical characteristics of the wound (e.g., exudate, granulation tissue, color)
- The dose-response and/or exposure-response relationships of repeat doses of GSK1278863 using PK/PD modeling for selected primary and exploratory endpoints (as data permit).

2.2. Study Endpoints

2.2.1. Primary Endpoints

- Clinical safety and tolerability data including spontaneous AE reporting, ECGs, vital signs, nurse/physician observation and clinical laboratory values after single and/or repeat doses of GSK1278863.
- Pharmacokinetic parameters of GSK1278863: SD: Cmax, tmax, terminal t_{1/2}, tlag, AUC(0-∞), AUC(0-t), (AUC(0-∞) and RD: Cmax, tmax, terminal t_{1/2}, AUC(0-t), (AUC(0-∞) and accumulation ratio), after single and/or repeat doses of GSK1278863, as data permit.

2.2.2. Exploratory Endpoints

After single doses of GSK1278863 (as data permit based on sampling feasibility):

- Change from baseline in gene expression (mRNA) in the DFU tissue.
- Change from baseline in biomarkers in the DFU (e.g., cytokine panel, protease panel).
- Change from baseline on bioburden in the DFU (e.g., rtPCR for bacterial load).
- Physical parameters of the wound (e.g., rate of healing, wound volume).
- Clinical characteristics of the wound (e.g., exudate, granulation tissue, color).

After repeat doses of GSK1278863 (as data permit based on sampling feasibility):

- Change from baseline in gene expression (mRNA) in the DFU tissue.
- Change from baseline in biomarkers of angiogenesis and blood flow and oxygen availability [e.g., skin perfusion pressure (SPP) and pulse volume (PV), hyperspectral imaging].
- Change from baseline in biomarkers in the DFU (e.g., cytokine panel, protease panel, macrophage quantification)
 - a. If the methodology can be validated at the site(s) cell proliferation and collagen turnover will be assessed.
- Change from baseline on bioburden in the DFU (e.g., rtPCR for bacterial load).

PWH115760

- Tissue concentrations of GSK1278863 in selected subjects as determined from micro-dialysis during RD, if feasible to conduct the assessment.
- Change from baseline on circulating biomarkers of systemic HIF activation in the blood (e.g., hemoglobin, hepcidin, EPO).
- Physical parameters of the wound following repeat doses of GSK1278863, for example:
 - a. Rate of wound healing (via planimetry).
 - b. Change in wound volume (Silhouette software).
 - c. Percentage of subjects with closure of the study DFU.
 - d. Time to DFU closure.
 - e. Time required to achieve a certain percent of wound closure.
 - f. Incidence of DFU closure.
- Clinical characteristics of the wound (e.g., exudate, granulation tissue, color).
- Correlation between GSK1278863 dose and/or exposure and parameters of pharmacodynamic activity, safety, and tolerability, as data permit.

Due to the termination of this project and the limitations of the data some of the exploratory endpoints have been modified for reporting as follows:

- Gene expression and qPCR data will be analysed by Target Sciences and the results will be summarized in a separate report.
- Instead of change from baseline, descriptive summaries will be created for the angiogenesis and blood flow and oxygen availability, the biomarkers in the DFU, the bioburden in the DFU, and biomarkers of systemic HIF activation in the blood.
- The only physical parameter to be evaluated is change in wound volume and area
- Correlation between GSK1278863 and PD and safety will not investigated further, unless multiple safety issues make is necessary

[figure not shown]
Given the time it takes to process the assay, the histology data will not be available for inclusion in the final data base at the time of database freeze. Therefore, this data will be analysed when it becomes available. If the results are available before CSR, then they will be included in the study report; otherwise, they will be included in an addendum to the study report or separate study report.

3. STUDY DESIGN

[figure not shown]
This first-time-in-human study of the topical formulation of GSK1278863 is designed as an initial exploration of the safety, tolerability, pharmacokinetic and pharmacodynamic effects. The study will be performed in a cohort of healthy volunteers and then in diabetics, including application both to healthy, intact skin, as well as to diabetic foot ulcers directly. This study includes two parts (Part A and Part B). Part A is designed to evaluate single applications of GSK1278863. Part A will include one cohort of healthy volunteers (intact skin) and approximately 3 cohorts of diabetic subjects with foot ulcer. Part B is designed to evaluate repeat applications of GSK1278863 in diabetics, both in the clinic and by subjects at home. Part B will include approximately 3 cohorts in which the concentration of drug applied will be determined by pharmacokinetic data from Part A and earlier cohorts in Part B. For both parts of the protocol, additional cohorts may be added as necessary to obtain relevant safety, pharmacokinetic or pharmacodynamic data.

Furthermore, for both Parts A and B, there will be at least one week between cohorts for review of safety, tolerability and PK data by the GSK study team (unblinded) and the Investigator (blinded). Pharmacodynamic data, where available, may be obtained for review. Enrollment to each cohort may be staggered (i.e., cohorts do not have to be enrolled as one group). However, all enrollments should occur within ~4 weeks for each cohort. Diabetic subjects, in either Part A or B, will require a two week run in period in which standard of care is given before treatment of the DFU with GSK1278863 or placebo in order to ensure the wound does not show a greater than 30% reduction in size.

PWH115760

Figure 1 Study Design/Schematic**Part A - Single Applications**

- Washout between periods is 10 days
- Cohort numbers and treatment letters in this example assume no optional cohorts used

Part B – 14-Day Repeat Applications

- Initiation of Part B may overlap with final cohort in Part A. Timing dependent upon Part A safety and PK data.

Subjects will be assigned to receive GSK1278863A or vehicle (placebo) in Part A and GSK1278863A or vehicle or SOC only (moist occlusion) in Part B in accordance with the randomization schedule generated by GSK, prior to the start of the study, using validated internal software.

Based on data from Part A it was decided that there would only be one cohort in part B.

3.1. Sample Size

There is no formal calculation of power or sample size in this study. Sample sizes are based on feasibility. A sample size of six subjects per active single dose (Part A), and twelve subjects per active repeated dose (Part B) completing the study are feasible sample sizes to provide sufficient safety and PK data for this FTIH study. The target sample size is set at 8 subjects per cohort in Part A, (6 on active treatment and 2 on placebo), and 16 per cohort in Part B, (12 on active treatment, 2 on placebo and 2 receiving standard of care). The sample size for the placebo at each dose level is set at two to avoid subject bias in safety assessment.

4. PLANNED ANALYSES

4.1. Interim Analyses

There will be no formal interim analysis; however, all preliminary safety, tolerability, and available pharmacokinetic data will be reviewed internally at GSK prior to each dose escalation (GSK study staff are unblinded).

4.2. Final Analyses

The final planned SAC analyses will be performed after all subjects have completed or withdrawn from the study and after the database freeze/unblinding is declared.

5. ANALYSIS POPULATIONS

All Subject Population: All subjects who receive at least one dose of study drug (including GSK1278863, placebo and standard care) will be included in the All Subject Population. Randomized subjects will only be excluded if there is clear documented evidence of failure to take any study medication. Subjects in the All Subject Population will be analyzed according to the treatment received and will be used for the reporting of safety and study population.

Enrolled: All participants who sign informed consent and for whom a record exists on the study database. This population will be used for the tables/listings of reasons for withdrawal before randomization and listings of AEs and SAEs for non-randomized participants.

Pharmacodynamic (PD) Population: All subjects who provide pharmacodynamic (PD) data will be included in the PD population. This population will be used in the evaluation of PD. For the change from baseline assessment, only those providing both evaluable baseline and post-dose values (so that the change can be calculated) will be included in the analysis. All subjects in the PD Population will be analyzed according to the treatment they actually received.

Pharmacokinetic (PK) Population: All subjects from whom a pharmacokinetic (PK) sample has been obtained and analyzed will be included in the PK population. This population will be used for reporting of PK concentration and the PK parameters.

6. HYPOTHESES AND TREATMENT COMPARISONS

This study is designed to evaluate the safety and tolerability of topical application of GSK1278863 in healthy volunteers and patients with diabetic foot ulcer following single dose (SD) and repeat dose (RD) administration. No formal hypothesis will be tested. For each primary pharmacokinetic endpoint, point estimates and corresponding

PWH115760

95% confidence intervals will be constructed for GSK1278863 and its metabolites for SD and RD respectively. Comparison of PD endpoints, including physical parameters of the wound, clinical characteristics of the wound, gene expression, biomarkers, bioburden, etc, will be performed with GSK1278863 versus placebo or standard care as data permit.

7. TREATMENT AND OTHER SUB-GROUP DESCRIPTIONS FOR DATA DISPLAYS

Randomisation		Final Data Display (i.e. HARP / other)
Code	Treatment Description	Treatment Description*
A	0.3 mg GSK1278863	300mg of 0.1% ointment to deliver 300µg of GSK1278863- SD
B	GSK1278863 Single Dose B	300mg of 1% ointment to deliver 3000µg of GSK1278863- SD
C	GSK1278863 Single Dose C	0.1% of GSK1278863 ointment at 25 mg/cm ² SD
D	GSK1278863 Single Dose D	1% of GSK1278863 ointment at 25 mg/cm ² SD
E	GSK1278863 Single Dose E	1% of GSK1278863 ointment at 100 mg/cm ² SD
R1r	GSK1278863 Repeat Dose R1r	1% of GSK1278863 ointment at 100 mg/cm ² RD
PR1r	Placebo	Placebo RD
P	Placebo	Placebo SD
Sr	Standard of Care	Standard of Care RD

* for dose applies to DFU patients, since the actual dose depends on the size of the wound, the treatment description should use a volume measure similar as used for Doses C and D once the actual dose formulation becomes available.

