4.2.1.4. Cohort 2 (Part A)

Cohort 2 will enroll DFU subjects who fulfill screening criteria. Subjects will be randomized to receive a single application of GSK1278863 or placebo in two dosing periods. The two dosing periods are intended to provide a 'within patient' comparison of PK between application to intact skin and to DFU. The first application will be made on intact skin, followed by a 10-day washout period. Blood for serial PK sampling will be collected out to 72 hours post-dose. After review of safety, tolerability and PK data, these subjects will then receive an application of the same dose directly to the DFU.

Subjects will come in to the clinic fasting early in the morning of Day 1 of each dosing period and will follow the same schedule as Cohort 1, with the exception that the first application will be on intact skin, and the application in the second dosing period will be directly to the DFU. See Section [4.6.1](#) for detailed timing of assessments and sampling.

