4.3. Treatment Assignment

This will be a single-blind study. Treatments will be blinded to subjects and the investigator site staff only. GSK study staff is not blinded.

Subjects will be assigned to receive GSK1278863A or vehicle (placebo) in Part A and GSK1278863A or vehicle or SOC only (moist occlusion) in Part B in accordance with the randomization schedule generated by GSK Discovery Biometrics, prior to the start of the study, using validated internal software.

Subjects will be randomized into the study by means of an interactive voice response system (IVRS) to receive one of the treatment regimens listed in the below tables ([Table 2](#) and [Table 3](#)).

Table 2 Part A Doses

Cohort	Regimen	Dose (mg)	Treatment Area by Period	
			1	2
1	P	Placebo ¹	Intact	Intact
	A	0.3mg		
	B	TBD ²		
2	P	Placebo	Intact	Wound
	C	TBD		
3	P	Placebo	Wound	N/A
	D	TBD		
4(or final)	P	Placebo	Wound	Intact
	E	TBD		
O (Optional) ³	P	Placebo	Wound	N/A
	F	TBD		

1. Placebo = vehicle
 2. Actual doses to be determined as preliminary PK data are reviewed and predicted exposures can be calculated.
 3. More than one optional cohort may be used.

Table 3 Part B Doses

Cohort ¹	Regimen	Dose (mg)
5	P	Placebo ²
	S	Standard of Care
	F ³	TBD
6	P	Placebo
	S	Standard of Care
	G	TBD
7	P	Placebo
	S	Standard of Care
	H	TBD

1. Cohort numbering may be different based on the number of cohorts conducted in Part A
2. Placebo = vehicle
3. Starting dose may be adjusted based upon evaluation of PK data from Part A

In Part A

For Cohorts 2 through 4, drug volume to be administered will be based on wound area. See Section 11 for details.

An example of planned doses of GSK1278863 and regimen designation for Part A is in [Table 4](#).

Table 4 Example Treatment Options

Cohort	Regimen/ Dosing Period	Dose (mg)	Treatment Area
1 (HVT)	P1	Placebo ¹	Intact Skin
	A	0.3 mg	Intact Skin
	P1	Placebo	Intact Skin
	B	TBD ²	Intact Skin
2	P1	Placebo	Intact Skin
	C1	TBD	Intact Skin
	P2	Placebo	Wound
	C2	TBD	Wound
3	P2	Placebo	Wound
	D	TBD	Wound
4(or final)	P2	Placebo	Wound
	E1	TBD	Wound
	P1	Placebo	Intact Skin
	E2	TBD	Intact Skin
O (Optional) ³	P2	Placebo	Wound
	F	TBD	Wound

1. Placebo = vehicle

2. Actual doses to be determined as preliminary PK data are reviewed and predicted exposures can be calculated.

3. More than one optional cohort may be used.

In Part B

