5. STUDY POPULATION

5.1. Number of Subjects

Enough subjects will be enrolled in Part A (Single Doses) such that approximately 32 subjects (~8 healthy volunteers in Cohort 1, and ~24 DFU subjects in Cohorts 2, 3 and 4) complete dosing and critical assessments. If optional cohort(s) are utilized, each cohort will enroll approximately 8 subjects (6 on active drug, 2 on placebo).

In Part B, enough subjects will be enrolled such that approximately 48 subjects in Part B (~16 DFU subjects per cohort) complete dosing and critical assessments (assumes approximately 3 cohorts).

Additional subjects/cohorts may be enrolled to allow for evaluation of additional dose levels, based on emerging data. The IRB will be informed if any additional cohorts (including optional cohorts) are included in the study based on local site requirements.

If subjects prematurely discontinue the study, additional subjects may be enrolled as replacement subjects and assigned to the same treatment sequence at the discretion of the GSK Medical Monitor in consultation with the Investigator.

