11.1. Drug Concentration Measures

Concentrations of GSK1278863 in plasma and its metabolites [M2, M3, M4, M5, M6 and M13] will be listed and summarised by treatment group and nominal time. Standard summary statistics will be calculated (i.e. mean and associated 95% confidence interval, standard deviation, median, minimum and maximum). Refer to the standard operating procedure, SOP-CPK-0001, and the guidance document, GUI-CPK-3001, for more information regarding the treatment of plasma concentrations below the assay's lower limit of quantification (NQ). For this study, when there is

PWH115760

more than one embedded NQ, NQ will be treated as zero rather than missing or truncated. Leading and tailing NQ will be treated per SOP.

Individual plasma concentration-time profiles and median/mean profiles by treatment group will be plotted. Each of the figures will contain one plot on the untransformed scale (i.e. a linear plot) and one plot on the log transformed scale (i.e. log-linear plot).

Plasma drug concentrations excluded from the PK analysis (i.e. PK parameter calculation) will be excluded from the summaries and figures. These concentrations will be flagged in the listing of PK concentration data.

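### SAP Section 7 labels carry no application site or population, so Part A adverse event and exposure tables as written mix intact skin with wound and set healthy-volunteer doses beside mainly DFU placebo

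*SAP*

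**What the plan says.** SAP Section 7 maps each randomisation code to the description used in final data displays. Code C becomes "0.1% of GSK1278863 ointment at 25 mg/cm ² SD". Code E becomes the 1% ointment at 100 mg/cm² single dose, and Part A placebo becomes Placebo SD. None of the three names the application site or the population.

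The protocol doses these groups on different sites. Cohort 2 (code C) receives intact skin in Period 1 and the wound in Period 2, to give a within-patient "comparison of PK between application to intact skin and to DFU". The final cohort (code E) receives the wound first and intact skin second. Cohort 1 (codes A and B) is healthy volunteers on intact skin, and Cohort 3 (code D) is wound only. Placebo subjects follow the schedule of their own cohort. Protocol Table 2 uses single codes with the treatment area shown by period. Protocol Table 4 uses site-specific codes (C1/C2, E1/E2, P1/P2) and is introduced by "An example of planned doses of GSK1278863 and regimen designation for Part A is in".

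The AE and exposure tables in SAP 14.1.2 use the All Subjects population, and no programming note splits them by site, period or population. SAP Section 10 says only that vital signs and ECGs are summarised by dose and time point. Exhibit G, the shell for wound and other pharmacodynamic summaries, has a Placebo DFU row and visits that carry the Part A period. Section 7 defines no such placebo group.

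**The concern.** Safety and tolerability in healthy volunteers and in DFU patients is the first primary objective of both documents. The Part A design addresses it by changing population and site one step at a time. An AE column that carries neither loses that information in the summary. A reader of the C or E column could not tell whether an event arose in the intact-skin or the wound period. A reader of A or B would see a placebo column made up mostly of patients with diabetes and an open ulcer, whose background events need not resemble those of healthy volunteers.

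This matters most for DFU patients' intact skin. The DFU-specific assessments in the Part A schedule, including the irritation scale, are done only when product is on the ulcer, apart from screening. Local tolerability on patients' intact skin therefore rests largely on AEs, and the AE tables are the ones without a site split.

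**Working it through.** **Inputs.** Allocation per Part A cohort is "6 on active treatment and 2 on placebo" (SAP 3.1). Planned size is "approximately 32 subjects (~8 healthy volunteers in Cohort 1, and ~24 DFU subjects in Cohorts 2, 3 and 4" (Protocol 5.1). Sites by cohort and period come from Protocol Table 2 and Sections 4.2.1.2 to 4.2.1.5. Four cohorts are assumed, with Cohort 4 as the final one. SAP Section 7 lists no optional Part A regimen.

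**Plan's own figure.** (6 + 2) × 4 cohorts = 32, made up of 8 healthy volunteers (1 × 8) and 24 DFU subjects (3 × 8). This reproduces the stated total.

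**Planned applications by SAP code.**

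| Cohort | Population | Period 1 | Period 2 |
|---|---|---|---|
| 1 | Healthy volunteers | intact: A 6, placebo 2 | intact: B 6, placebo 2 |
| 2 | DFU | intact: C 6, placebo 2 | wound: C 6, placebo 2 |
| 3 | DFU | wound: D 6, placebo 2 | none |
| 4 | DFU | wound: E 6, placebo 2 | intact: E 6, placebo 2 |

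**Active columns.** C holds 6 intact + 6 wound = 12 applications, and so does E. A and B are all healthy-volunteer intact skin, and D is all wound. Only C and E mix sites.

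**Placebo SD, by subject.** 4 × 2 = 8 subjects: 2 healthy volunteers and 3 × 2 = 6 DFU. The DFU share is 6/8 = 75%. One optional wound cohort would make it 8/10 = 80%, and two would make it 10/12 = 83%.

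**Placebo SD, by application.** Healthy-volunteer intact 2 + 2 = 4; DFU intact 2 + 2 = 4; DFU wound 2 + 2 + 2 = 6; total 14, of which 10 (71%) are in DFU patients.

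**Does period separate the sites?** For C and E it does: Period 1 is intact for C and wound for E, and Period 2 is the reverse. For placebo it does not:
- Period 1 holds 2 healthy-volunteer intact, 2 DFU intact and 4 DFU wound applications.
- Period 2 holds 2 healthy-volunteer intact, 2 DFU wound and 2 DFU intact applications.

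Both periods mix site and population, so a placebo table split by period alone remains mixed.

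**Like-for-like placebo.** The placebo group matching A and B is 2 subjects, not 8.

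**The case against.** The strongest reply is that no SAP sentence says sites or populations will be combined. The AE and exposure tables refer to standard shells whose columns the SAP does not reproduce. Exhibit G points the other way, with period-labelled visits and a DFU placebo row, and SAP 8.5 takes Cohort 2's baseline from Period 2. All data are to be listed (SAP 8.1), and with about 6 active subjects per cohort a reviewer can read site from cohort and period. No AE comparison is specified either: "No formal hypothesis will be tested", and "There is no formal calculation of power or sample size in this study".

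Much of this stands, and it rules out several stronger readings.

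- *The SAP discarded binding regimens.* Table 4 is offered as an example, and the SAP codes match Table 2. What was lost is Table 2's treatment area by period.
- *An event in C or E can never be tied to a site.* Listings, and by-visit tables that keep the period, can do it. The gap is in the summary tables.
- *Wound irritation scores are pooled over sites.* They are taken only in wound periods, apart from screening.
- *Drug concentrations are averaged over sites.* SAP 11.1 says they "will be listed and summarised by treatment group and nominal time", which might suggest this. The display note for that table is by treatment and visit time, which can separate C and E. The SAP's revision history also records Part A exposure to that date as below the quantification limit. Little rests on this.
- *A stated drug effect would be hidden.* The documents give no background AE rates, so no such figure can be supported.

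What the reply does not meet is that Section 7 is the stated key for displays and nothing in the safety specifications restores the split. Listings do not replace the planned summaries of a primary objective.

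**Conclusion.** The point holds as a labelling fault in the planned safety summaries. As written, the AE and exposure tables give C and E columns that are half intact skin and half wound (6 and 6 planned applications each), and a single-dose placebo column that is 75% DFU by subject beside healthy-volunteer regimens A and B. Section 7 and Exhibit G also cannot both be followed for placebo.

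The consequence is a misleading side-by-side description; no statistical test is biased, because none is planned. The counts are planned values for four cohorts. Protocol 4.2.1 lets diabetic subjects enter more than one cohort, and SAP 8.1 reports them under their first subject number, so the number of distinct DFU placebo subjects could be below 6. The conclusion also assumes that the standard shells take their columns from Section 7, which is what that section is for.

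**What to change.** In SAP Section 7:

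- Split Part A placebo into healthy-volunteer and DFU groups.
- Add site (intact or wound, derived from cohort and period) to the C, E and DFU placebo labels, for at least the AE and exposure tables.
- State that each AE is assigned to the dosing period in which it starts.
- Use the same labels in Exhibit G.

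A pooled DFU placebo column may be kept as a supplement.

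No new data are needed, since site follows from cohort and period. The work is in the label table and the programming. The price is small columns: about 2 healthy-volunteer placebo subjects, 4 DFU intact placebo applications and 6 DFU wound placebo applications. The gain is like-for-like description. It gives no power to detect a difference, and the report should not suggest that it does.
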